9.0 Local Number of Subjects

The target enrollment for the case-control portion (Aims 1 & 2) is 120 subjects and 60 subjects for the clinical trial (Aim 3), for a total of 180 subjects across all aims. We plan to recruit a total of 60 subjects with Fragile X Syndrome with full FMR1 mutations (>200 CGG repeats; at least partial FMR1 gene methylation). Of these FXS subjects, 40 will be recruited for the case-control portion and 20 will be recruited into the clinical trial. The overall project will recruit an additional two cohorts of control subjects for a total of 60 IQ-, sex-, and chronologically aged matched non-syndromic (i.e., idiopathic) ASD controls, and 60 sex-and chronologically aged matched TDCs. Following completion of the case-control portion, subjects and their guardians may be asked to participate in the clinical trial portion of the study.

Retention Plan: We do not anticipate a high drop-out rate since almost all testing is non-invasive, and each portion of the study (case-control and clinical trial, respectively) can be completed in 2 visits, with ample time allowed between visits. Thus, we expect close to 90% retention of all recruited subjects. Subjects unable to complete study procedures or who fail to consent/withdrawal following enrollment will be replaced to maintain our enrollment target of 180 total subjects.

10.0 Recruitment

Recruitment Methods and Materials

Potential participants may be recruited for the study at CCHMC, from the general public, and at special community events or lectures. In some instances, subjects who have consented to be contacted for

future studies may be sought if they qualify for this study. Participants may also be recruited from local and national databases intended for recruitment, EPIC queries, and OCTR database queries.

Fragile X subjects will be recruited from the Cincinnati Fragile X Research and Treatment Center by treating physicians and their staff. The clinical team will present the project to patients and family members when they are at our clinics or treating physicians may contact them directly about their interest in participation.

Participants with a history of Developmental Disability will be recruited from the CCHMC Developmental Disabilities Psychiatry Service (inpatient and outpatient services), the CCHMC Division of Developmental and Behavioral Pediatrics outpatient clinics, other CCHMC outpatient clinics, CCHMC inpatient units, at special events and from the general public.

The study will be advertised in hospital/clinic and general public areas via print, email, electronic and social media. The Cincinnati Fragile X Research and Treatment Center will be sending out a monthly newsletter providing resources, research findings, upcoming events, and research opportunities to families who have expressed interest in clinic/research; information about research opportunities will also be distributed in the form of a brochure. All recruitment materials mentioned above will be IRB-approved prior to send-out.

Interested families or potential participants may contact the research team directly by the phone number or email address given in the advertisements, at which time a research coordinator will follow up by phone or email. When individuals contact our research staff or provide consent to be contacted, we will provide them with basic information regarding study procedures and aims, inform them that this research is voluntary, and answer any questions about the study. Family and medical history will be reviewed in person or over the phone to determine study eligibility. If no exclusionary factors are identified in the review of family and medical history, then subjects will be scheduled for a meeting to obtain informed consent.

Potential participants and their families may be given the option to have a practice cap/beanie mailed to them to aid with sensory familiarity in preparation for a potential future visit. For some participants with a history of Developmental Disability, the optional EEG tasks may present an uncomfortable sensory experience, especially to those unfamiliar with the EEG cap. To allow for adequate practice and preparation time, this option may be presented before the potential participant has been consented to the study. The practice beanies fit snugly around the head, offering a similar sensation to a real EEG cap. If the family already owns a similar cap the subject can practice with it they may be asked to use that instead. The caps will not be used to screen subjects and are only being provided to increase subjects' comfortability with EEG. Subjects who opt to receive a practice cap are not required to practice wearing the cap prior to the first visit. It will be explained to potential subjects/caregivers that receiving the practice cap does not require them to later enroll in the research study or to complete EEG tasks at a subsequent research visit. The practice caps are of negligible monetary value and are not believed to unduly influence subjects' consideration of participating in the study.

Compensation

Subjects will receive \$50 for each completed visit. If a participant cannot complete any study visits, they will be compensated at a rate of \$15/hr. based on what they have completed.

Payment will be in the form of a reloadable debit card (ClinCard). We will provide the card and load money onto the card after each completed visit. We will also administer a handout that will explain how to use it.

Because this research study involves payment for participation, we are required by federal Internal Revenue Service (IRS) rules to collect and use participants' social security or tax ID number (SSN) in order to track the amount of money that we pay. We will only use the participants' SSN to keep track of how much money we pay to them and their SSN will not be used as part of this research.

Families traveling significant distance to our clinic may be reimbursed for travel costs at the discretion of the PI. This may include mileage, hotel, airfare and/or other associated costs.

11.0 Withdrawal of Subjects

Any participant may be discontinued from the study at the discretion of the investigators if this is deemed to be in the best interest of the participant or if they are not compliant with study-specific requirements. A subject may voluntarily withdraw from the study at any time and for any reason. If a subject withdraws, at his or her request or at the request of his or her caregiver or legal representative, the reason(s) should be documented in the subject's source document. Any research information recorded for, or resulting from, participation in this research study prior to the date that the subject formally withdrew their consent will be retained and may continue to be used and disclosed by the investigators for research purposes; however, no new data will be collected.

12.0 Risks to Subjects

Confidentiality of records and results: The neurophysiological, medical, psychological, and behavioral measures will be made anonymous and labeled only by a unique identification number. Appropriate precautions will be taken to protect the confidentiality of all data. All subjects will be informed of this, including the HIPAA privacy of information act.

Behavioral and cognitive testing: There are minimal risks anticipated to participating in observational, clinical behavioral assessments. In the rare case that an individual might become overly fatigued or distressed during the assessment session, the session will be discontinued and rescheduled. Evaluation procedures are designed to be compatible with the attention span of a person with intellectual disability, greater activity level, and need for access to his or her parents or guardians. The NIH Cognitive Toolbox specifically created downward developmental extensions to accommodate for these needs. In addition, specialized procedures will be accompanied with specialized approaches such as using social stories and visual aids. There will be praise for task attention and overall emphasis on reducing language demands. The clinical investigators have extensive experience working clinically with developmentally disabled patients and their families.

EEG: EEG testing is considered minimal risk. The most common risk associated with these tasks is boredom. The EEG nets do not use an electrode gel, but rather a saline solution and sponges which has a very low risk of skin irritation. The candidate and EEG technicians are highly experienced with doing EEG with sensitive populations such as children and subjects with neurodevelopmental disorders.

13.0 Potential Benefits to Subjects

Direct benefit to study participants is minimal. The major immediate benefit of participation in the proposed studies would be screening for symptoms of ASD and related disorders. Subjects may receive benefit from a complete evaluation including diagnostic, psychiatric, psychological, and medical evaluations in the form of a report. For individuals who are diagnosed with ASD or new diagnosis of FXS, appropriate referrals can be made if desired by study participants and their guardians. Caregivers and guardians may receive information regarding understanding the subject's behavior which may benefit them. We may also provide resources to connect them to local, regional, and national support organizations for FXS. Families and subjects may appreciate contributing to the discovery of innovative FXS treatments that will benefit other individuals. Healthy subjects often have various motivations and different rewards for participating in the study. Some subjects will be primarily motivated by the participant compensation. Others may want to participate to learn more about their skills or are personally committed to developmental disability research.

14.0 Data Management and Confidentiality

Data Storage and Sharing

All records will be handled in a confidential manner. All hard copy data will be stored in code-labeled binders in locked storage facilities with limited access. Any electronic files containing patient identifiers will be either stored on a secure server or password protected database. Only the Principal Investigator and his designees will have access to hard-copy or electronic data.

Unique numeric identifiers that do not include any PHI will be assigned to each participant. Identification numbers will code data entered for computer analysis, and the designated study staff will keep all names and code numbers in a password-protected folder. EEG scans recordings will be anonymized by using only the participant study IDs and the date and time of scanning/recording and will be stored on a secure server.

Sociodemographic information collected from this research may be utilized to create a Universal Identification Number (GUID) for the National Database for Autism Research (NDAR). Data that is collected from each research visit may be shared with NDAR. Before this data is sent to NDAR, information such as name and birthplace city will be removed and replaced with a GUID.

Research data gathered as part of this study may be shared and provided to other investigators affiliated with the Neurobehavioral and Neurology Research Teams at CCHMC for the purpose of data sharing. If information is requested by an investigator, the PI must approve the request. If participants are enrolled in multiple or linked studies, their research data will be shared across studies to reduce participant burden and avoid duplication of procedures. All shared data will be de-identified, and results will be published as group data without the use of characteristics that would identify individual participants.

Quality Control

At point-of-entry, data values will undergo consistency edits (e.g., ID validation, range verification, duplicate detection) and personnel will be required to correct errors. Data management staff will run logic error programs to check for accuracy and irregularities within and across data structures and within and across sites. Quality assurance checks will be conducted regularly by site personnel as well as by data management staff. Regularly scheduled, and as needed, communications between the study team, the neuroimaging team and PI will clarify any inconsistencies and ambiguities in the data.

Data Analysis

Power Analysis: **Aim 1A:** Based on differences in PPF in FXS vs. TDC in our resting state EEG data, we expect an effect size of approximately .8 to 1.1, similar to effect sizes in low gamma power and N1 amplitudes in FXS^{10, 12, 90, 91}. **Aim 2:** The effect size for WLI differences between structured and random conditions is approximately .8⁵³. The primary comparisons for both **Aim 1A** and **Aim 2** will be between diagnostic groups, FXS vs. TDC and FXS vs ASD. Therefore, to be statistically conservative, the nominal alpha of .05 will be divided by 4, i.e. .0125 per hypothesis. Using the available FXS vs. TDC effect size of 0.8, 40 subjects in each of the three diagnostic groups yields 84.3% power at a level of significance = .0125. Effects size data for FXS vs. ASD for these measures is not available but may be estimable for future studies. **Aim 3:** This aim is novel, without a strong basis for estimating an effect size. AAE effect size of PPF enhancement (vs. sham) in our preliminary data is between .89 and .97 (obtained peak frequencies of 9.3 to 9.6 Hz). For the within-groups crossover, an AAE trial to detect treatment differences in a 2 X 2 crossover design (20/group) yields approximately 80% power to identify group differences with an effect size of .9 at an alpha of 0.05.

Statistical analysis: PPF (**Aim 1A**) and WLI (**Aim 2**) were selected as primary response variables since they will be individually optimized as starting parameters in **Aim 3**. Planned comparisons include FXS vs. TDC and FXS vs. ASD. FXS vs. TDC will be of primary interest, but confirmation of FXS vs. ASD can weaken the inference that differences in intellectual ability and genetic liability alone account for group difference. **Covariates:** FXS vs. TDC model will include age, sex, and non-verbal IQ. FXS vs. ASD will additionally include co-occurring psychiatric diagnoses, psychiatric medication(s) (4 categories), and SRS score. A group by sex interaction will be added to each model given known sex

differences in FXS¹⁵. **Aim 1B:** Murine data will consist of a parallel model to Aim 1A with three neurodynamic variables (PPF, event duration, and event number) and independent variable of group (KO or WT; 80 in each group). **Aim 3:** A linear model with repeated measures will test a 2-treatment, 2-period, 2-sequence balanced-crossover design (Williams, 1989) with Kenward-Roger adjustment⁹² applied. Further, as in Aim 1A and 2, two separate models will be examined for FXS vs. TDC and FXS vs. ASD. The responses of interest in Aim 3 are 40Hz ITC and WLI change (AAE vs. sham). The fixed effects of diagnostic group, treatment, the interaction between diagnostic group and treatment, treatment sequence, and period will be examined. Potential carryover effects will also be assessed. **Covariates:** Covariates for each comparison will be identical to models for Aim 1A and 2 above. The adjusted (least squares) means for the diagnostic group by treatment combination will allow to compare within and between diagnostic groups. Within the FXS group, for example, the treatment effect will be by testing the contrast (FXS treatment – FXS sham) at the 0.05 level of significance.

Exploratory analyses: **Aim 1A:** Other neurodynamic response variables (event rate and event duration) and chirp response (40Hz ITC and gamma ERSP) will be modeled as PPF. If the sex x diagnostic group interaction is significant ($p < .05$), subsequent post-hoc inter-diagnostic comparisons will be made for each sex. Lastly, for Aim 1A, the five variables representing neurodynamics and chirp response (PPF, event rate, event duration, 40 Hz ITC, and gamma ERSP) will be examined as a multivariate response across two paradigms (rest and chirp). As in the models above, diagnostic group will be the independent variable along with the appropriate covariates as described above. **Aim 1C:** To identify which FXS genotype (males with or without mosaicism and females) has similar alterations in neurodynamic variables as the Fmr1-/- KO (vs. WT) we will derive 95% confidence intervals for the effect sizes for each of the three neurodynamic variables for each of the three FXS subgroups (vs. their respective matched controls) and compare to the confidence interval for the effect size based on the Fmr1-/- KO vs. WT comparison. Lastly, significant differences between the FXS effect sizes and the murine effect size will be explored using bootstrap methodology where the resampling will be within each subgroup (human and mouse).

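### The four primary case-control tests at a fixed .0125 are valid, but Holm's step-down would reject at least as much under the same .05 guarantee, for a small wording change

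*Combined protocol and SAP*

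**What the plan says.** The power paragraph in section 14.0 (Data Analysis) states that the primary comparisons for Aims 1A and 2 "will be between diagnostic groups, FXS vs. TDC and FXS vs ASD", and that "to be statistically conservative, the nominal alpha of .05 will be divided by 4, i.e. .0125 per hypothesis". The statistical analysis paragraph names the outcomes: PPF (Aim 1A) and WLI (Aim 2) "were selected as primary response variables since they will be individually optimized as starting parameters in" Aim 3. Two outcomes by two contrasts gives the four hypotheses behind the divisor.

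The power statement is made at that fixed level: "40 subjects in each of the three diagnostic groups yields 84.3% power at a level of significance = .0125", with d = .8. For the other contrast, "Effects size data for FXS vs. ASD for these measures is not available".

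The statistical analysis paragraph ranks the contrasts informally: "FXS vs. TDC will be of primary interest, but confirmation of FXS vs. ASD can weaken the inference" that intellectual ability and genetic liability alone explain the group difference. It sets no testing order and gives no test level for Aims 1A and 2. The .0125 appears only in the power paragraph. No step-down, fixed-sequence or gatekeeping rule for these tests appears anywhere.

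**The concern.** Dividing .05 equally by four and holding every test at .0125 is a single-step Bonferroni rule. It keeps the strictest threshold even after other hypotheses in the family have been rejected. Holm's procedure starts at the same threshold and relaxes it only after each rejection, so it can recover findings that the fixed rule leaves just short.

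The FXS vs ASD comparisons are the ones most exposed. They have no effect-size basis in the plan, they must meet the same .0125, and the plan relies on them to support its reading of the FXS vs TDC difference. If the FXS vs TDC tests succeed as the plan expects, a step-down rule would ease the threshold for the FXS vs ASD tests.

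**Working it through.** **Inputs from section 14.0.** Family level .05; four hypotheses; 40 per group; d = .8 for FXS vs TDC; stated power 84.3% at .0125. Sidedness is not stated.

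**Inputs assumed, because the documents do not give them.** FXS vs ASD effect, taken from 0 to .8; correlation between PPF and WLI, taken as .3 (0 and .5 as checks). The WLI effect for FXS vs TDC is also assumed: the .8 that the plan cites for WLI is the difference between structured and random conditions, not between diagnostic groups.

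**1. The plan's own figure.** .05 / 4 = .0125. Two-sample t-test, df = 2 × 40 − 2 = 78, noncentrality = .8 × √(40/2) = 3.578. At two-sided .0125 the power is 84.3%, as stated. One-sided gives 89.9%, so the plan's figure is two-sided.

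**2. Holm's thresholds.** Order the four p-values. Compare the smallest with .05/4 = .0125, the next with .05/3 = .0167, then .05/2 = .025, then .05, and stop at the first failure. Power of a single d = .8 test at each threshold:

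| Threshold | Power |
|---|---|
| .0125 | 84.3% |
| .0167 | 86.8% |
| .025 | 89.9% |
| .05 | 94.2% |

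**3. Nothing is lost.** If k of the p-values are at or below .0125, they are the k smallest, and each meets a Holm threshold that is at least .0125. Holm therefore rejects all of them.

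**4. The bound is the same.** With m true nulls, the first true null that Holm could reject is met when at least m hypotheses remain, so its threshold is at most .05/m. The chance that any of m true nulls has p ≤ .05/m is at most m × .05/m = .05, whatever the dependence. This covers the shared FXS group and needs only valid p-values, so it carries over to the covariate-adjusted models.

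**5. Size of the gain.** Simulation of three groups of 40 with unadjusted t-tests, correlation .3, and FXS vs TDC d = .8 on both outcomes. Power per test, fixed .0125 → Holm:

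| FXS vs ASD effect (assumed) | FXS vs TDC | FXS vs ASD |
|---|---|---|
| 0 | 84% → 86% | null |
| .2 | 84% → 86% | 5% → 9% |
| .5 | 84% → 88% | 38% → 52% |
| .8 | 84% → 92% | 84% → 92% |

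If only PPF FXS vs TDC is large (.8), with WLI FXS vs TDC .3 and FXS vs ASD .2, power for PPF FXS vs TDC moves only from 84.3% to 84.5%. Correlations of 0 and .5 give similar per-test gains where they were run (FXS vs ASD 0, .5 and .8). The chance of at least one rejection is the same under both rules, because the first threshold is the same.

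**6. Actual family-wise error.** With all four nulls true it is about 4.6% under both rules. With FXS vs TDC d = .8 and FXS vs ASD d = 0 it rises from about 2.5% to about 4.4%. With three effects at .8 and one true null it rises from about 1.2% to about 4%. It stays below .05 throughout.

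**The case against.** The strongest case against is that nothing is broken. The plan uses a valid rule, says that it is meant to be conservative, and its power figure is right. That stands.

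A reader might infer that the fixed .0125 buys no extra error protection. That would be wrong. Only the guaranteed bound is shared. When some effects are real and others null, the fixed rule's actual family-wise error is lower, and Holm's additional false rejections would fall on the comparisons that are truly null, which could be FXS vs ASD. A check under the global null alone would miss this, because the two rules coincide there.

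A reader might also take the larger gains as the expected ones. The documents do not support that. They give no FXS vs ASD effect and no group-difference effect for WLI, and the simulated tests omit the covariates and the group-by-sex interaction of the planned models.

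Other points have some weight:

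- Holm does not use the stated priority of FXS vs TDC, which a sequence or gatekeeping rule would. But a strict sequence can lose rejections that the present rule makes; Holm cannot.
- The fixed rule lets each aim be concluded on its own and has matching 98.75% intervals (1 − .0125). Holm makes each decision depend on all four p-values.
- Section 4.0 lists further Aim 1 primary outcomes (event rate, event duration, 40 Hz ITC, asynchronous gamma power), while section 14.0 models event rate, event duration, 40 Hz ITC and gamma ERSP as exploratory. The family should be settled first. Holm works for a family of any size.

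**Conclusion.** The point holds as a cheap improvement. The current rule is valid and 84.3% is correct, so neither a flaw in error control nor a need to change the sample size follows. Holm on the same four p-values never rejects fewer hypotheses and keeps the .05 guarantee under any dependence, at the price of a higher actual error rate within that guarantee.

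The gain for FXS vs TDC is 2 to 8 percentage points per test if d = .8 holds on both outcomes. For FXS vs ASD it is 4 points at d = .2, 14 at .5 and 8 at .8. If only one of the four effects is large, the gain for that test is close to nil. The dominance and the error bound are certain. The sizes are conditional on the assumed effects, correlation .3 and unadjusted t-tests.

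**What to change.** In the statistical analysis paragraph of section 14.0, state that the four p-values (PPF and WLI, each for FXS vs TDC and FXS vs ASD) are tested by Holm's step-down at family-wise .05, with thresholds .0125, .0167, .025 and .05. In the power paragraph, replace the fixed level per hypothesis with this rule, and describe 84.3% as the power at Holm's first threshold, a lower bound for the same test and effect. Make the change before any results are seen.

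The cost is about a sentence in each place, with no added participants or data. The downside is that simultaneous intervals no longer match the tests exactly. Report ordinary 95% intervals labelled as unadjusted, and note that one may exclude zero for a hypothesis that Holm does not reject.

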8.0 Inclusion and Exclusion Criteria

Inclusion Criteria (all aims):	FXS	ASD	TDC
Aged 5-15 years, inclusive	X	X	X
Patient has full FMR1 mutation confirmed by genetic testing	X		
Have no known genetic mutation		X	
Have documentation of ASD diagnosis		X	
Score ≤ 15 on SCQ screen		X	

Be in good health per investigator		X	X
Patient has met normal developmental milestones			X
Patient has no family history of heritable neuropsychiatric disorders			X
Patient has an IQ greater than 85 on the Stanford-Binet			X
Score ≤8 on an SCQ screen			X

Exclusion Criteria (all aims):	FXS	ASD	TDC
Patient has auditory or visual impairments that cannot be corrected	X	X	X
History of substance abuse or dependence within the past 6 months	X	X	X

Vulnerable Populations

- Inclusion of women and minorities: We will include males and females in numbers consistent with the distribution expected in the clinic populations. We will not exclude any participant based on race or ethnicity. The distribution of minorities will be consistent with the distribution expected in Cincinnati.
- Inclusion of children: A central aim of the proposed research is to evaluate the underlying mechanisms responsible for brain development in children with FXS. This can only be done by studying affected individuals in that age group. The minimum age of 5 was chosen because of the level of cooperation required to complete procedures, and the upper age limit of 15 was chosen because of common age-related changes in behavior and brain function beyond that age.
- Persons with Cognitive Impairment or other limited decision-making capacity: To be inclusive and most generalizable in our study findings, and because some elements of our protocol can be completed with minimal cognitive requirements, such as event-related potential (ERP) monitoring of cortical responses to tones, we will recruit any study-eligible patient with Fragile X Syndrome regardless of level of cognitive disability into as many study components as they can complete. We will recruit all FXS patients who we believe can complete study procedures.

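### The 84.3% power for FXS vs TDC is that of an unadjusted t-test; the planned model adjusts for non-verbal IQ, which eligibility ties to group, and the power of that test is not given

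*Combined protocol and SAP*

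**What the plan says.** Section 14.0, Power Analysis, sets alpha at .05/4 = .0125 per hypothesis for Aims 1A and 2. For PPF it says: "Based on differences in PPF in FXS vs. TDC in our resting state EEG data, we expect an effect size of approximately .8 to 1.1". It then takes the lower end, "Using the available FXS vs. TDC effect size of 0.8", and concludes that "40 subjects in each of the three diagnostic groups yields 84.3% power at a level of significance = .0125". It mentions no covariate, no variance explained and no correlation between group and covariates.

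Section 14.0, Statistical analysis, describes the model: "FXS vs. TDC model will include age, sex, and non-verbal IQ", plus a group by sex interaction. It names FXS vs TDC as the main comparison. The same covariates carry into Aim 3: "Covariates for each comparison will be identical to models for Aim 1A and 2 above".

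Section 8.0 requires of TDCs only: "Patient has an IQ greater than 85 on the Stanford-Binet". For FXS it says "we will recruit any study-eligible patient with Fragile X Syndrome regardless of level of cognitive disability". Section 9.0 matches the ASD controls on IQ, sex and age, but the TDCs on sex and age only.

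For WLI, the power analysis also cites an effect of about .8, but that effect compares the structured with the random syllable stream. It is not a difference between diagnostic groups.

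**The concern.** A power figure should belong to the test that will be run. In a linear model, adjusting for a covariate changes the precision of the group effect in two ways. Precision improves if the covariate explains outcome variance within groups. It worsens if the covariate is correlated with group, because less independent information about group is left. Age and sex are matched, so they cost little. Non-verbal IQ is not matched, and the eligibility rules push it apart between FXS and TDC. The net effect depends on the IQ gap and on the variance explained, and the plan states neither.

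84.3% is the only power figure for the main comparison of Aims 1A and 2. If the adjusted test has much less power, a null result could mean no difference or simply too little IQ overlap to estimate one. The plan specifies no output to tell these apart. The within-participant AAE vs sham contrasts in Aim 3 are not affected.

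**Working it through.** **1. Reproducing the stated figure.** Inputs from Section 14.0: d = 0.8, 40 per group, alpha .0125. For a two-sided two-sample t-test, the noncentrality is d × √(n/2) = 0.8 × √20 = 3.58 on 78 df. Power is **84.33%**, which matches 84.3%. Other readings do not match: normal approximation 86.0%, one-sided t 89.9%, error pooled over three groups 84.9%. The plan does not name the test, so the unadjusted t-test is inferred from this match.

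**2. The planned test.** The model has six parameters (intercept, group, age, sex, group by sex, non-verbal IQ), so df = 80 − 6 = 74. Losing 4 df alone costs almost nothing (84.2%). The IQ imbalance enters through a variance inflation factor:

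- VIF = [pooled within-group IQ variance + (mean difference/2)²] / pooled within-group IQ variance
- noncentrality = d/√(1 − R²) × √(20/VIF), where R² is the share of within-group outcome variance explained by all covariates together

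**3. Assumptions, because the documents give no IQ distributions.** TDC IQ is taken as normal (100, 15) truncated above 85, giving mean 104.3 and SD 11.9. Non-verbal IQ is assumed to be distributed likewise. Five FXS distributions are tried. The adjusted effect is held at d.

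Example, FXS 70/20: pooled variance = (11.9² + 20²)/2 = 270.8. Half the gap = (104.3 − 70)/2 = 17.15, squared 294.1. VIF = (270.8 + 294.1)/270.8 = 2.09. Noncentrality at d = 0.8, R² = 0: 0.8 × √(20/2.09) = 2.47. Power is 47%.

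**4. Results for PPF (power, %).**

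| FXS IQ mean/SD | VIF | d=0.8, R²=0 | d=0.8, R²=30% | d=0.95, R²=0 | d=1.1, R²=0 |
|---|---|---|---|---|---|
| 60/15 | 3.68 | 25 | 38 | 37 | 51 |
| 70/20 | 2.09 | 47 | 66 | 65 | 80 |
| 80/20 | 1.55 | 63 | 81 | 80 | 92 |
| 85/20 | 1.34 | 70 | 87 | 86 | 95 |
| 90/25 | 1.13 | 79 | 92 | 92 | 98 |

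The 0.95 column is the midpoint of the plan's .8 to 1.1.

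**5. Break-even.** 84.33% on 74 df needs a noncentrality of 3.58, so the required R² = 1 − 20d²/(3.58² × VIF), floored at 0. In the order of the table:

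- d = 0.8: 73, 52, 35, 26, 12%
- d = 0.95: 62, 33, 9, 0, 0%
- d = 1.1: 49, 10, 0, 0, 0%

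**6. Checks.** A simulation of the full model in age- and sex-matched pairs (6,000 replicates, d = 0.8, nothing explained) gives 23.7, 46.0, 61.0, 68.0 and 77.0%. The same model without IQ gives 84.0%. Moving the TDC mean before truncation through 95, 100, 105 and 110, with FXS 70/20, gives 50, 47, 43 and 39%.

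**7. If the adjusted effect is not 0.8.** Take an IQ gap of 2 within-group SDs (VIF = 1 + 2²/4 = 2) and an unadjusted difference of 0.8. A within-group IQ–outcome correlation of 0.1 in the direction of the group effect leaves an adjusted effect of 0.8 − 0.1 × 2 = 0.6 and power of about 26%. With the opposite sign the adjusted effect is 1.0 and power about 73%.

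**The case against.** The strongest case on the other side has five parts.

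- **The effect size may already carry the adjustment.** If 0.8 was converted back from the test statistic of an IQ-adjusted model, it already contains the variance inflation, and power would be about 84.2% under a similar IQ gap. This stands as a possibility. Section 14.0 does not say, and Section 3.0 describes the controls in the preliminary data only as matched on age and sex. It is a reason to state the basis of the effect size.
- **The range rests on assumed IQ distributions and cannot show that the study is underpowered.** Correct. The plan also used the bottom of its effect range and a divided alpha. At d = 1.1 with nothing explained, three of the five scenarios exceed 84.3% and a fourth gives 80%.
- **The 30% column is not always coherent with the plan's own range.** If IQ itself explained 15% of the variance at FXS 70/20 (a gap of 2.09 SD), an adjusted effect of 0.8 would imply an unadjusted one of about 0.8 + √0.15 × 2.09 = 1.6, in the same direction. That column is best read as variance explained by age or sex. This weakens the favourable cases, not the point.
- **FXS vs ASD, with IQ-matched controls, is the plan's own check on intellectual ability.** True, and it helps interpretation, but it supplies no power for FXS vs TDC.
- **A simple two-group calculation is a common approximation in a descriptive case-control study, and error control is untouched.** Also true. The approximation is harmless when covariates are balanced; here one is unbalanced through eligibility and matching.

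**Conclusion.** The point holds. The stated figure is arithmetically right for an unadjusted test and is not the power of the planned one. That the plan omits the IQ imbalance and the variance explained is certain from the text. The size of any loss is not established by the documents. Under the assumptions above, power at d = 0.8 with nothing explained is 25% to 79%. It recovers to 84.3% or more only where the IQ gap is small, the true adjusted effect is nearer 1.1, or the covariates explain a good deal of the outcome. All of these figures concern PPF. For WLI, group-comparison power is not established by the plan's calculation or by this one, because no FXS vs TDC effect size for WLI is given.

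**What to change.** In Section 14.0, Power Analysis:

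1. Replace 84.3% with the power of the IQ-adjusted test, as a range under stated assumptions for the FXS–TDC IQ gap and for the variance explained by all covariates. Alternatively, label 84.3% as the power of the unadjusted contrast only.
2. State whether .8 to 1.1 is an unadjusted or an adjusted effect.
3. State that the figure applies to PPF, and that FXS vs TDC power for WLI is not established.

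In Section 14.0, Statistical analysis, keep the planned model and pre-specify two supportive outputs that use no alpha:

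- the FXS vs TDC contrast without non-verbal IQ, keeping age, sex and group by sex;
- an IQ-overlap check: the IQ distribution by group, and the number of FXS participants within the TDC range.

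Which model is primary is the sponsor's choice of estimand and is left alone here. The cost is some wording and two extra outputs. Sample size, data collection, the primary model, the Aim 3 models and the exploratory models do not change. The downside is probably a less favourable stated power.
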